8.1.1. Study Completion and End of Trial

This study will be considered complete (that is, the scientific evaluation will be complete [study completion]) following the evaluation of final OS data (refer to Figure JPBM.8.2) as determined by Lilly. Investigators will continue to follow the study schedule for all patients until notified by Lilly that study completion has occurred.

"End of trial" refers to the date of the last visit or last scheduled procedure for the last patient. The end of trial occurs after study completion and after the last patient has discontinued study treatment and completed continued access period follow-up (Figure JPBM.8.2).

Abbreviations: OS = overall survival; PFS = progression-free survival.

Figure JPBM.8.2. Study period and continued access period diagram.

8.1.2. Continued Access Period

After study completion, all patients who are on study treatment and who are eligible for the continued access period will be unblinded. Patients receiving study treatment and experiencing ongoing clinical benefit may continue to receive study treatment in the continued access period until one of the criteria for discontinuation is met (Section 7.3.1). During the continued access period, placebo will no longer be administered, and crossover will not be permitted. Lilly will notify investigators when the continued access period begins.

Patients who are in short-term follow-up when the continued access period begins will continue in short-term follow-up until the 30-day short-term follow-up visit is completed. Long-term follow-up does not apply.

Patients who are in long-term follow-up when the continued access period begins will be discontinued from long-term follow-up.

During the continued access period, all AEs, SAEs, and study drug exposure will be reported on the CRF. Serious adverse events will also be reported to Lilly Global Patient Safety (see Section 10.3.1). In the event that an SAE occurs, Lilly may request additional information (such as local laboratory results, concomitant medications, and hospitalizations) in order to evaluate the reported SAE.

Investigators will perform any other standard procedures and tests needed to treat and evaluate patients; however, the choice and timing of the tests will be at the investigator's discretion. Lilly will not routinely collect the results of these assessments.

8.2. Discussion of Design and Control

A randomized, controlled design is being used in this study. Randomization minimizes systematic bias in the selection and assignment of patients to study therapy and provides justification for inferential statistical methods to be used on data from this study. Using an appropriate concurrent control arm enables direct statistical estimation of benefits and harms due to study therapy and minimizes bias in the assessment and interpretation of observed treatment effects. Patients will be stratified for differences in factors thought to be associated with clinical outcomes to further reduce the potential for bias and improve the power of the analyses. Assessment of bias is further minimized by the use of a double blind and placebo control (see Section 9.3).

Investigational treatment administration in this study is double-blind; that is, patients, investigational sites, and the sponsor study team do not have immediate access to investigational treatment assignments for any patients. This design feature minimizes potential bias due to knowledge of patient's treatment during evaluation of study endpoints, at the patient level or aggregated across patients.

9. Treatment

9.1. Treatments Administered

The following treatments will be administered in this study:

- Experimental Arm A: LY2835219 150 mg orally every 12 hours plus either anastrozole 1 mg or letrozole 2.5 mg orally every 24 hours on Days 1 to 28 of a 28-day cycle
- Control (Placebo) Arm B: Placebo orally every 12 hours plus either anastrozole mg or letrozole 2.5 mg orally every 24 hours on Days 1 to 28 of a 28-day cycle.

Blinded study drug is defined as LY2835219 or placebo. Study treatment is druned as blinded study drug and/or NSAI.

The specific NSAI (anastrozole or letrozole) administered to patients is do rmined by the investigator. Patients should remain on the same NSAI throughout according exceptional cases, in the absence of evidence of PD, the investigator may discuss the ge in NSAI with the Lilly CRP. NSAI is a co-administered standard-of-care treath and the investigator should refer to the NSAI label (that is, Patient Information Leafle Package Insert, or Summary of Product Characteristics). Table JPBM.9.1 shows the treatment regularity

Table JPBM.9.1. Treatment Regimens/Dosing Schedule

Regimen	Period/Cycle	Dose Day
Experimental Arm A		
LY2835219	Treatment/28-day cycle	150 mg PO every 12 hours on Days 1-28 ^a
Anastrozole		1 mg PO every 24 hours on Days 1-28 ^b
or	Treatment /28-day cycle	or
Letrozole		2.5 mg PO every 24 hours on Days 1-28 ^b
Control (Placebo) Arm B		. (2)
Placebo	Treatment/28-day cycle	PO every 12 hours on Days 1-28 ^a
Anastrozole		1 mg PO every 24 hours on Days 1-28 ^b
or	Treatment /28-day cycle	or
Letrozole		2.5 mg PO every 24 hours on Days 1-28b

Abbreviations: ECG = electrocardiogram; PK = pharmacokinetic; NSAI = nonsteroidal aromatase inhibitor; PO = orally.

The investigator or his/her designee is responsible for the following:

- explaining the correct use of the drugs and planned duration of each individual's treatment to the patient/site personnel/legal representative,
- verifying that instructions are followed properly,
- maintaining accurate records of study drug dispensing and collection (including the coadministered NSAI doses taken by the patient),
- and returning all unused medication supplied by Lilly to Lilly or its designee at the end of the study.

Note: In some cases, sites may destroy the material if, during the investigator site selection, the evaluator has verified and documented that the site has appropriate facilities and written procedures to dispose of clinical trial materials.

Patients will be instructed to contact the investigator as soon as possible if they have a complaint or problem with the study drug so that the situation can be assessed.

^a On Cycle 1 Day 1 only, patients should take one single dose of blinded study drug and initiate chronic every-12-hours dosing on Cycle 1, Day 2.

^b For PK and ECG purposes, NSAI should be administered at the same time (or up to 20 minutes after) the morning dose of blinded study drug through Cycle 4, Day 1. Subsequently, the interval between administration of blinded study drug and NSAI may be adjusted based on the judgment of the investigator.

9.2. Materials and Supplies

LY2835219 or placebo (blinded study drug) will be supplied as capsules for oral administration. Blinded study drug capsules should be stored according to the product label, and not opened, crushed, or dissolved. Blinded study drug will be labeled according to the country's regulatory requirements.

Where required, letrozole and anastrazole will be supplied by Lilly and labeled according to country regulatory requirements. Letrozole and anastrazole should be stored according to the product label and will be provided as anastrazole 1-mg or letrozole 2.5-mg tablets.

Investigators should instruct patients to store the blinded study drug and NSAI in the original package provided and in a location inaccessible to children.

9.3. Method of Assignment to Treatment

Upon obtaining informed consent, site personnel should access the interactive web response system (IWRS) which will assign a patient number. Patients who meet all criteria for enrollment will be randomly assigned to receive either LY2835219 or placebo. Assignment to treatment groups will be determined by a computer-generated random sequence using the IWRS. Sites will be prompted to enter the specific NSAI at time of randomization.

Randomization will be stratified by the following: nature of disease (visceral metastases versus bone-only metastases versus other), and prior (neo)adjuvant endocrine therapy (aromatase inhibitor therapy versus other versus no prior endocrine therapy).

The IWRS will be used to assign LY2835219 or placebo and distribute NSAI supplied by Lilly. Site personnel will confirm that they have located the correct study medication packages by entering a confirmation number found on the packages into the IWRS.

The period between randomization to blinded study drug and the first dose (Cycle 1, Day 1) should not exceed 7 days.

9.4. Selection and Timing of Doses

Blinded study drug will be taken orally every $12 (\pm 2)$ hours on Days 1 through 28 of a 28-day cycle, for a total of 56 doses per cycle. During all cycles, blinded study drug should be taken at approximately the same times each day. If a patient misses or vomits a blinded study drug dose, that dose should be omitted.

Anastrozole or letrozole will be administered orally every 24 hours (±2) on Days 1 through 28 of a 28-day cycle for a total of 28 doses per cycle. For PK and electrocardiogram (ECG) purposes, anastrozole or letrozole should be administered at the same time as (or up to 20 minutes after) the morning dose of blinded study drug through Cycle 4, Day 1. Subsequently, the interval between administration of blinded study drug and anastrozole or letrozole may be adjusted based on the judgment of the investigator. If a patient misses or vomits an anastrozole or letrozole dose, that dose should be omitted.

A cycle is defined as an interval of 28 days plus any subsequent delay prior to start of the next cycle. A delay in the start of a cycle due to holidays, weekends, bad weather, or other unforeseen circumstances will be permitted up to 7 days and not counted as a protocol deviation). For each 28-day cycle, a total of 56 doses of blinded study drug will be dispensed. In exceptional cases, for planned delays (including but not limited to vacation or holidays), additional study treatment may be dispensed.

A patient may continue to receive study treatment until she meets 1 or more of the specified reasons for discontinuation (as described in Section 7.3.1).

9.4.1. Special Treatment Considerations

9.4.1.1. Dose Adjustments and Delays

9.4.1.1.1. Dose Adjustments

9.4.1.1.1.1 Blinded Study Drug

Blinded study drug dose adjustments as outlined in Table JPBM 9.2 are allowed both within a cycle and between cycles. Blinded study drug must be reduced sequentially by one dose level.

For patients requiring dose reduction(s), any re-escalation to a prior dose level is permitted only after consultation with the Lilly CRP.

Table JPBM.9.2. Dose Adjustments for Blinded Study Drug

Dose Adjustment Level	Oral Dose	Frequency
0	150 mg	Every 12 hours
1	100 mg	Every 12 hours
2	50 mg	Every 12 hours

Blinded study drug must be discontinued if further dose reduction is required beyond 50 mg every 12 hours. In the event that blinded study drug must be discontinued, a patient may continue to receive anastrozole or letrozole.

9.4.1.1.1.2. Anastrozole or Letrozole

Per NSAI labels, dose adjustment for anastrozole or letrozole is not applicable, as only a single-dose strength is approved for each medication. In exceptional cases in the absence of evidence of PD, the investigator may discuss a change in the specific NSAI administration (for example, switching from anastrozole to letrozole) with the Lilly CRP. In the event that anastrozole or letrozole must be discontinued, a patient may continue to receive blinded study drug per the investigator's clinical judgment.

9.4.1.1.2. Dose Suspension (within a Cycle) and Cycle Delay

Both dose suspension (within a cycle) and cycle delay are permitted. When a dose suspension or cycle delay occurs related to toxicity (defined as an AE possibly related to study treatment per

investigator judgment), the blinded study drug and/or NSAI may be suspended or delayed as determined by the investigator's judgment.

Study treatment may be held up to 14 days within a cycle or at start of next cycle to permit sufficient time for recovery from the toxicity. If a dose suspension occurs within a cycle, the investigator may resume blinded study drug dosing at the same dose level for the remainder of the cycle or at reduced dose (assuming resolution to at least Grade 1 for non-hematological and at least Grade 2 for hematological toxicity). If the patient experiences the same toxicity with the same or greater severity (CTCAE grade) requiring a dose suspension within a cycle or at start of the next cycle, the patient must be dose reduced and not re-challenged a second time at the prior dose level

Patients not recovering from toxicity within 14 days should be considered for discontinuation of the blinded study drug and/or co-administered NSAI. In exceptional circumstances, a delay >14 days is permitted upon agreement between the investigator and the Lilly CRP and blinded study drug dose adjustment is to be considered.

In the event of a cycle delay due to logistical reasons (for example, due to patient availability), the patient should continue on study treatment if the patient has adequate drug supply. If a patient's treatment is interrupted as a result of not having sufficient drug supply, the cycle may be delayed up to 7 days (and not be considered a protocol violation). In exceptional circumstances, a delay >7 days is permitted upon agreement between the investigator and the Lilly CRP.

The start of a cycle may be delayed, or a current cycle interrupted, to allow a patient with a locoregionally recurrent breast cancer rendered operable by study treatment to receive surgery \pm radiotherapy. For additional information, refer to Section 9.6.1.

9.4.1.1.3. Hematologic Toxicity

If a patient experiences Grade 4 hematologic toxicity, then dosing must be suspended (until the toxicity resolves to either baseline or at least Grade 2) and the dose of blinded study drug must be reduced by one dose level as outlined in Table JPBM.9.2.

If a patient experiences Grade 3 hematologic toxicity, then dosing must be suspended (until the toxicity resolves to either baseline or at least Grade 2) and the dose of blinded study drug may be reduced by one dose level as outlined in Table JPBM.9.2 at the discretion of the investigator.

Before the start of each cycle, hematologic toxicity must resolve to either baseline or at least Grade 2.

9.4.1.1.4. Nonhematological Toxicity

If a patient experiences ≥Grade 3 nonhematologic toxicity, then blinded study drug and/or NSAI dosing must be suspended (until the toxicity resolves to either baseline or at least Grade 1) and the dose of blinded study drug must be reduced by one dose level as outlined in Table JPBM.9.2.

If a patient experiences persistent or recurrent Grade 2 nonhematologic toxicity (except diarrhea; refer to Section 9.4.1.1.4.1) that does not resolve with maximal supportive measures within 7 days to either baseline or at least Grade 1, then blinded study drug and/or NSAI dosing may be suspended (until the toxicity resolves to either baseline or at least Grade 1) and the dose of blinded study drug may be reduced by one dose level as outlined in Table JPBM.9.2 at the discretion of the investigator.

Before the start of each cycle, nonhematologic toxicity (except alopecia and fatigue) must resolve to either baseline or at least Grade 1.

9.4.1.1.4.1. Diarrhea

A patient experiencing diarrhea requiring hospitalization (irrespective of grade, that is, requiring intravenous [IV] rehydration) or severe diarrhea (Grade 3 or 4; see Attachment 9) must have study treatment suspended (until the toxicity resolves to either baseline or at least Grade 1) and must have the blinded study drug dose reduced by one dose level as outlined in Table JPBM.9.2.

If a patient experiences persistent or recurrent Grade 2 diarrhea that does not resolve with maximal supportive measures (refer to Section 9.6.5) within 3 days to either baseline or at least Grade 1, then study treatment should be suspended (until the toxicity resolves to either baseline or at least Grade 1) and the dose of blinded study drug may be reduced by one dose level as outlined in Table JPBM.9.2 at the discretion of the investigator. If the same dose level was resumed and diarrhea recurs despite maximal supportive measures, the dose of blinded study drug must be reduced by one dose level as outlined in Table JPBM.9.2.

9.5. Blinding

This is a double-blind study.

To preserve the blinding of the study, a minimum number of Lilly personnel will see the randomization table and treatment assignments before the study is complete. Access to unblinded data/documents will be controlled by restricting access to the data/documents in Lilly's data and statistical warehouse. Any changes to this unblinding plan may be described in a protocol amendment, the Statistical Analysis Plan (SAP), and/or a separate unblinding plan document.

Efficacy information will not be shared between sites until the study is completed. Upon overall study completion (see Section 8.1.1), investigators may unblind patients to study treatment assignment.

9.5.1. Unblinding at Interim Analyses

Interim analyses for safety and efficacy will be conducted, using unblinded data, under the guidance of an independent Data Monitoring Committee (DMC). The DMC will consist of at least 3 members, including at least 1 clinician and 1 statistician. The DMC will communicate any recommendations based on interim analysis to the Lilly Senior Management Designee (SMD). If necessary, the SMD may form an Internal Review Committee (IRC) to review and act

upon the recommendations of the DMC. See Section 12.2.14 for details on the conduct of interim analyses.

9.5.2. Emergency Unblinding

In case of an emergency, the investigator has the sole responsibility for determining if unblinding of a patient's treatment assignment is warranted. Patient safety must always be the first consideration in making such a determination. If the investigator decides that unblinding is warranted, the investigator should make every effort to contact the Lilly CRP prior to unblinding a patient's treatment assignment unless this could delay emergency treatment of the patient. If a patient's treatment assignment is unblinded, Lilly must be notified immediately.

Emergency unblinding for AEs must be performed through the IWRS. This option may be used ONLY if the patient's acute well-being requires knowledge of the patient's treatment assignment.

All calls resulting in an unblinding event are recorded and reported by the IWRS. If the investigator or patient becomes unblinded, that patient will be discontinued from study treatment and will undergo postdiscontinuation follow-up (Attachment 1). Long-term follow up procedures will be followed until death or study completion.

9.5.3. Inadvertent Unblinding

Every effort will be made to blind both the patient and the investigator to the identity of the treatment, but the inadvertent unblinding of a patient may occur. A double-blind study design is known to be imperfect in the oncolytic setting because the potential for individual unblinding exists due to treatment-related signs and symptoms. If an investigator, site personnel performing assessments, or patient is unblinded, the unblinding will not be sufficient cause (in and of itself) for that patient to be discontinued from study therapy or excluded from any safety or efficacy analyses.

Additionally, there may be ethical reasons to have the patient remain on the study treatment. For patients to continue on study treatment in the event of unblinding, the investigator must obtain specific approval from a Lilly CRP for the patient to continue in the study.

9.6. Concomitant Therapy

Appropriate documentation of all forms of premedications, supportive care, and concomitant medications must be captured at each visit in the eCRF. Concomitant medications and supportive care therapies must also be documented at the time of discontinuation and at the 30-day short-term follow-up visit.

With the exceptions listed in the sections below, therapies for cancer (including hormonal anticancer therapies, chemotherapy, and immunotherapy) will not be permitted while patients are on study treatment. Use of megestrol acetate as an appetite stimulant is not permitted.

The results from an in vitro human recombinant cytochrome P450 (CYP) phenotyping study indicate that oxidative metabolism of LY2835219 is primarily catalyzed by CYP3A.

Radiolabeled human disposition study indicates that LY2835219 is mostly cleared by oxidative metabolism and therefore inhibitors and or inducers of CYP3A may alter the metabolism of LY2835219. Based on these findings, grapefruit juice as well as inducers (for example, phenytoin or carbamazepine) and strong inhibitors of CYP3A4 should be substituted or avoided if possible (Attachment 8). All patients may receive supportive therapy with dexamethasone, preferably ≤7 days, if clinically indicated. Patients requiring more than 7 days of dexamethasone therapy will not incur a protocol deviation.

In addition, in vitro studies in primary cultures of human hepatocytes indicate that LY2835219 might inhibit the metabolism of CYP2B6 substrate drugs in vivo in humans. Based on this finding, bupropion and efavirenz, which are sensitive CYP2B6 substrates, should be substituted or avoided if possible.

9.6.1. Surgery and/or Radiotherapy for Locoregionally Recurrent Breast Cancer

A patient with locoregionally recurrent breast cancer may receive surgery \pm radiotherapy if study treatment renders the tumor operable. However, such a patient should not receive study treatment for the period beginning at least 7 days prior to surgery and continuing until at least 14 days after completion of surgery \pm radiotherapy to allow for tissue healing and recovery. There is no restriction on the duration of this period without study treatment and, after this period ends, study treatment may resume. Importantly, a patient who receives surgery \pm radiotherapy for locoregionally recurrent breast cancer is not considered noncompliant and does not incur a protocol deviation.

9.6.2. Radiotherapy

Except as described in Section 9.6.1, radiotherapy is not permitted without permanent discontinuation from study treatment. Except for a patient with locoregionally recurrent breast cancer rendered operable by study treatment who subsequently undergoes surgery + radiotherapy, all other patients requiring radiotherapy should discontinue permanently from study treatment and have a tumor assessment of the lesion(s) before receiving radiotherapy.

9.6.3. Supportive Care

Patients should receive full supportive care to maximize quality of life. Patients will receive supportive care as judged by their treating physician. If it is unclear whether a therapy should be regarded as supportive care, the investigator should consult the Lilly CRP. Use of any supportive care therapy should be reported on the eCRFs.

9.6.4. Growth Factor

Growth factors may be administered in accordance with ASCO guidelines (Smith et al. 2006; Rizzo et al. 2008).

9.6.5. Supportive Management for Diarrhea

In the event of diarrhea, supportive measures should be initiated as early as possible. These include the following:

- At the first sign of loose stools, the patient should initiate anti-diarrheal therapy (e.g. loperamide) and notify the investigator for further instructions and appropriate follow-up.
- Site personnel should assess response within 1 to 3 days.
- If diarrhea does not resolve with anti-diarrheal therapy within 3 days to either baseline or Grade 1, then dosing should be adjusted as outlined in Section 9.4.1.1.1.1 and Table JPBM.9.2.
- Patients should also be encouraged to drink fluids (e.g., 8 to 10 glasses of clear liquids per day).

In potentially severe cases of diarrhea, the measuring of neutrophil counts and body temperature and proactive management of diarrhea with antidiarrheal agents should be considered.

If diarrhea is severe (requiring IV rehydration) and/or associated with fever or severe (Grade 3 or 4) neutropenia, broad-spectrum antibiotics such as fluoroquinolones must be prescribed.

Patients with severe diarrhea or any diarrhea associated with severe nausea or vomiting should be carefully monitored and given fluid (IV hydration) and electrolyte replacement.

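### For Grade 2 diarrhea unresolved after 3 days, Protocol Section 9.6.5 points sites to the dose-reduction ladder, while Section 9.4.1.1.4.1 calls for suspension with reduction optional; the two must be reconciled.

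*Protocol*

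**What the plan says.** Protocol Section 9.6.5 (Supportive Management for Diarrhea, under Concomitant Therapy) sets this trigger: "If diarrhea does not resolve with anti-diarrheal therapy within 3 days to either baseline or Grade 1". No grade is named. The action follows directly: "then dosing should be adjusted as outlined in Section 9.4.1.1.1.1 and Table JPBM.9.2".

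The cited Section 9.4.1.1.1.1 states that dose adjustments from the table "are allowed both within a cycle and between cycles" and that "Blinded study drug must be reduced sequentially by one dose level". Table JPBM.9.2 lists three levels (150, 100 and 50 mg every 12 hours). The section also requires consultation with the sponsor's physician before any re-escalation, and permanent stopping of blinded drug if a step below 50 mg would be needed. It mentions neither diarrhea nor suspension.

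Protocol Section 9.4.1.1.4.1 (Diarrhea) deals with persistent or recurrent Grade 2 diarrhea that does not settle on maximal supportive measures, citing Section 9.6.5 for those measures: "within 3 days to either baseline or at least Grade 1, then study treatment should be suspended". A one-level reduction is then permitted at the investigator's discretion. It becomes compulsory in one case: "If the same dose level was resumed and diarrhea recurs despite maximal supportive measures". Grade 3 or 4 diarrhea, and diarrhea needing hospitalization, have a separate rule in the same section: suspension and reduction are both mandatory, with no 3-day wait.

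**The concern.** Diarrhea is the first-named common adverse event in the Protocol's Introduction (Section 5), so sites will use these instructions often. The two sections share the 3-day limit and the same recovery target (baseline or Grade 1), but they direct the site differently. Someone managing diarrhea from Section 9.6.5 alone is sent to a table of dose levels and is not told to suspend. Someone working from Section 9.4.1.1.4.1 is told to suspend and may restart at the same level.

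What is at stake is first the consistency of an operative safety instruction. The second issue is exposure data. Dose reductions, omissions and dose intensity are reported outputs (Protocol Sections 12.2.5 and 12.2.12; SAP Section 6.11.1), and part of their variation could reflect which section a site consulted. A reduction is also not easily reversed: there are only two steps below the starting dose, and going back up requires consultation with the sponsor's physician.

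**Working it through.** This is a comparison of texts; the plan states no figure to reproduce.

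**Side by side, for Grade 2 diarrhea unresolved at 3 days**

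| Element | Section 9.6.5 | Section 9.4.1.1.4.1 |
|---|---|---|
| Trigger | Not back to baseline or Grade 1 within 3 days of anti-diarrheal therapy; grade not named | Persistent or recurrent Grade 2, not back to baseline or Grade 1 within 3 days on the Section 9.6.5 measures |
| Suspension | Not mentioned, nor in the section and table it cites | *Should* be suspended until recovery |
| Dose of blinded drug | *Should be adjusted* under the ladder | *May* be reduced; compulsory on recurrence after the same level is resumed |
| Drugs covered | The cited ladder concerns blinded drug only | Study treatment, defined in Section 9.1 as blinded drug and/or NSAI |
| Cross-reference | To 9.4.1.1.1.1 and Table JPBM.9.2; none to 9.4.1.1.4.1 | To 9.6.5 for supportive measures |

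**Why the overlap is Grade 2.** Failure to return to Grade 1 implies Grade 2 or higher. Grades 3 and 4 have their own mandatory rule, which leaves Grade 2 as the range in which the two texts compete.

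**Three courses a site could take at a first episode**

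1. Suspend, then resume at the same level. This fits Section 9.4.1.1.4.1. It does not fit Section 9.6.5 if an adjustment means a move on the table, and dose levels are all the table contains.
2. Reduce one level without suspending. This fits Section 9.6.5 but not Section 9.4.1.1.4.1.
3. Suspend, then reduce. This fits both, but gives up the discretion that Section 9.4.1.1.4.1 grants.

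If diarrhea recurs after the same level was resumed, both texts lead to a lower dose. The disagreement over reduction is therefore confined to the time before such a recurrence.

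**Size of one disputed step.** From Table JPBM.9.2: (150 − 100) / 150 = 33% of the dose.

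**A smaller wording point inside Section 9.4.1.1.4.1.** Its mandatory rule opens: "A patient experiencing diarrhea requiring hospitalization (irrespective of grade, that is, requiring intravenous [IV] rehydration) or severe diarrhea". Hospitalization is explained as the need for IV rehydration, but IV fluids can be given without admission. The text does not say whether that case meets the trigger, and the grade definitions in Attachment 9 do not mention IV fluids.

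**The case against.** The strongest reply is that this is an incomplete cross-reference and not a contradiction. Section 9.6.5 says dosing is to be *adjusted*, not *reduced*. The cited section says adjustments are allowed, and its one-level-at-a-time sentence governs how to step down, not when. Silence on suspension in a supportive-care section does not forbid it, and Section 9.4.1.1.2 already provides for suspension, and for resuming at the same or a lower dose, for any toxicity. On the usual principle that a specific rule outranks a general pointer, Section 9.4.1.1.4.1 prevails. Because that section leaves reduction to the investigator, some variation between sites is built in anyway.

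Much of this stands. A reader might infer that Section 9.6.5 orders a reduction at the first episode and that the sections cannot both be obeyed. The wording does not go that far, and suspending followed by reducing complies with each. The specific-over-general principle, however, requires the site to know that the specific rule exists, and Section 9.6.5 sends it elsewhere. The cited number differs by one digit from that of the diarrhea section, so a miscitation is possible, although Table JPBM.9.2 does sit in the section cited.

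A reader might also infer two competing dose triggers for severe diarrhea, since Section 9.6.5 has: "If diarrhea is severe (requiring IV rehydration) and/or associated with fever or severe (Grade 3 or 4) neutropenia". The documents do not support that. This sentence governs antibiotics, and the neighboring one governs monitoring and fluids. The Grade 3 or 4 wording in Section 9.4.1.1.4.1 governs dosing. They attach to different actions.

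**Conclusion.** The point holds as an inconsistency in an operative dosing instruction for an expected toxicity. For Grade 2 diarrhea unresolved at 3 days, the sections differ on suspension (absent against *should*) and on reduction (*should be adjusted* against *may be reduced*), and the section most likely to be consulted for diarrhea management does not lead to the diarrhea dosing rule. It is worth correcting but modest, because one course of action satisfies both texts.

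No patient count can be given. The documents do not state a rate of persistent Grade 2 diarrhea at 150 mg every 12 hours. It is tempting to size the problem from the 25.7% in the Introduction (Section 5), but that is Grade 3 diarrhea at 200 mg with NSAI: a different dose, and a grade outside the overlap. Nor do the documents make diarrhea alone the reason for the 150 mg dose; the Introduction credits clinical and PK findings together with preliminary safety data.

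No effect on alpha, power, sample size or the intention-to-treat comparison is claimed. The conclusion rests on reading an adjustment under Table JPBM.9.2 as a change of dose level, and on the protocol text approved in September 2014. The SAP refers to amendments (a) and (b), which were not available, so a later correction cannot be excluded.

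**What to change.** Reconcile Protocol Sections 9.6.5, 9.4.1.1.4.1 and 9.4.1.1.1.1 so that a site reading any of them finds one instruction on suspension and reduction for diarrhea unresolved at 3 days, and sees which drugs it covers. Correcting the cross-reference in Section 9.6.5 is one way to do this. Which clinical rule is kept is the sponsor's decision.

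In the same edit, state in Section 9.4.1.1.4.1 whether IV rehydration without admission meets its mandatory trigger. Before drafting, check whether amendment (a) or (b) has already changed these passages.

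The cost is a sentence or two of protocol text, with no added procedures or data and no change to the SAP.
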